11.2.4 Interim Analysis

No formal interim analysis is planned for this study. An IDMC will be convened for this study, primarily to monitor safety at regular intervals. An IDMC charter, detailing all aspects of the IDMC's scope of review and procedures will be described in a separate document. In addition, ongoing safety data will be reviewed by the Sponsor in a blinded fashion for each age cohort. Interim PK/PD data will be analyzed by an unblinded designee (Section 5.1).

11.2.5 Pharmacokinetic/Pharmacodynamic Analyses

Population PK modeling will be conducted to estimate PK parameters (e.g., C_{max}, AUC, t_{1/2}, CL/F and Vz/F). Effects of intrinsic factors, including age and weight, and extrinsic factors, including formulation, on the PK parameters may be evaluated.

The exposure and platelet count data will be used to establish a population PK/PD model. Covariates on the PD parameters, such as Baseline platelet count and age, may be evaluated. If the dose for any permitted concomitant ITP medications taken at Baseline by the subject has changed during the Core Phase, the platelet count data after the change will not be included in the analysis. The adult data may be combined with the pediatric data to provide more robust evaluation. The PK parameters and PK/PD relationship in the pediatric population may be compared to those in the adult population.

Enrollment in subsequent cohorts will be staggered and the exact doses may be modified during the study based on PK/PD analysis (e.g., PK/PD modeling) of emerging data or safety data. If unanticipated exposure and platelet counts are observed, the doses may be modified to best match exposure-response relationships observed in adults.

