5 PHARMACOKINETIC AND SAFETY DATA REVIEW

5.1 Ongoing Data Review

All available PK and safety data through Week 10 of the study will be reviewed by the Sponsor and/or the Sponsor's designee (e.g., for unblinded PK data) for the first 10 subjects enrolled into Cohort 1 prior to opening enrollment into the Core Phase for subjects in Cohort 2. Likewise, all available PK and safety data through Week 10 will be reviewed by the Sponsor and/or the Sponsor's designee (e.g., for unblinded PK data) for the first 10 subjects enrolled into Cohort 2, prior to opening enrollment into the Core Phase for Cohort 3. Enrollment will not stop during this data review period.

As the study progresses and data become available, the pediatric PK/PD model will be updated with emerging data in order to confirm the appropriate dose of avatrombopag in each cohort. The PK/PD model will be updated after each age cohort is fully enrolled, but without stopping enrollment for remaining cohorts. The dose of avatrombopag may be modified during the study based on results of the PK and safety data review.

Safety data will be reviewed on an ongoing basis and new enrollment may be paused for any serious unexpected and related AEs that occur (Figure 2).

The exact doses of avatrombopag may be modified during the study based on PK/PD analysis of emerging PK/PD and safety data.

The Sponsor and the project team will remain blinded during the ongoing safety data review. Interim PK/PD analyses will be conducted by an unblinded designee.

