8.3 Permitted ITP Concomitant Background Medications

The following medications are permitted as concomitant background medications as long as they are taken at a stable dose for the specified amount of time prior to Day 1/Visit 2. The dose/frequency as well as any dose changes must be recorded in the eCRF.

- Corticosteroids or azathioprine/6-mercaptopurine taken at a stable dose for at least 30 days before Day 1/Visit 2.
- MMF, CsA, sirolimus, or danazol taken at a stable dose for at least 90 days before Day 1/Visit 2.

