8.4 Concomitant ITP Medication Dose Reduction

Any permitted concomitant ITP medications taken at Day 1/Visit 2 by the subject during the Core Phase may be down titrated in order to maintain the subject's platelet count between $\geq 50 \times 10^9/L$ and $\leq 150 \times 10^9/L$. Downward concomitant ITP medication titration will be at the discretion of the Investigator, all dose changes must be recorded in the eCRF.

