8.6 Rescue Therapies

Subjects may receive rescue therapy at the discretion of the Investigator if there is an urgent need to increase platelet count, such as in the case of life-threatening thrombocytopenia, in the opinion of the Investigator, clinical signs and symptoms suggesting a potential bleed (e.g., wet purpura) or a major bleed. All rescue medications, including dose and frequency, must be recorded on the eCRF.

Rescue therapy may include:

- The addition of any *new* ITP medication or medication to treat thrombocytopenia, such as:
 - Corticosteroids
 - o IVIg
 - o Anti-D
 - Platelet transfusion
- Any *increase in the Day 1/Visit 2 dose* of a concomitant ITP medication.
- TPO-RAs are not allowed as rescue therapy.

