7.4 Efficacy Analysis

Unless otherwise stated, all primary and secondary efficacy endpoints defined in Section 3.2.1 will be analyzed for the FAS and PPS.

For the efficacy evaluation of the platelet count responses, platelet counts assessed by local labs will be used. Platelet counts collected via the central lab will be used in the safety assessments of

clinical laboratory tests.

The methods used for efficacy analysis for the Core Phase are summarized in Error! Reference source not found.3. All Cochran-Mantel-Haenzel (CMH) tests at alpha=0.05 within each age cohort will be performed adjusting for baseline platelet count category ($\leq 15 \times 10^9 / L \text{ vs} > 15 \times 10^9 / L$). For the CMH test in the overall group, the test will be performed adjusting for age cohort and baseline platelet count category. Fisher's exact test will be used if the number of durable platelet responders is spare in the strata (less than 3 in a specific subgroup). Durable platelet response with 2-sided 95% exact binomial (Clopper-Pearson) confidence interval (CI) will be provided. The difference in response rate (avatrombopag – placebo) with 2-sided 95% CI (Wald) will also be provided.

Subjects without sufficient data for the determination of response status (i.e., responder versus non-responder) will be treated as non-responders in the analysis.

For the primary efficacy endpoint determination, a subject must have remained in the Core phase through at least Week 10 (to have at least 6 weeks of platelet count data starting from week 5 to either week 12 if the subject completes the core phase or the last week if the subject prematurely terminates the core phase). If a subject terminates the Core phase prior to Week 10, they would be considered a non-responder for the primary efficacy endpoint.

Endpoint	Analysis Method
Primary Efficacy Endpoint	
Durable platelet response defined as proportion of subjects achieving at least 6 out of 8 weekly platelet counts $\geq 50 \times 10^9 / L$ during the last 8 weeks of the 12 week treatment period in the Core Phase in the absence of rescue medication. In the case of rescue medication being used, platelet count assessments from the start date of rescue medication up until 4 weeks after the end date of rescue medication will be excluded from analysis.	CMH test

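### The PK/PD data-exclusion rule in Protocol 11.2.5 covers rescue by raising a background ITP drug but not rescue by a new drug or transfusion, so as written it leaves rescue-affected platelet counts in the model that informs later cohorts' doses

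*Protocol*

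**What the plan says.** **The model and its one exclusion.** Protocol 11.2.5 states: "The exposure and platelet count data will be used to establish a population PK/PD model". Its only data exclusion is conditional: "If the dose for any permitted concomitant ITP medications taken at Baseline by the subject has changed during the Core Phase", then "the platelet count data after the change will not be included in the analysis". No end date is given for that exclusion.

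**What counts as background.** Protocol 8.3 opens with "The following medications are permitted as concomitant background medications as long as they are taken at a stable dose" and lists corticosteroids, azathioprine/6-mercaptopurine, MMF, cyclosporine, sirolimus and danazol. Protocol 8.5 bars immunoglobulins and platelet transfusion on study except as rescue.

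**What counts as rescue.** Protocol 8.6: "Subjects may receive rescue therapy at the discretion of the Investigator if there is an urgent need to increase platelet count". It names two kinds: adding a new ITP drug (examples are corticosteroids, IVIg, anti-D and platelet transfusion) and raising the Day 1 dose of a concomitant ITP drug.

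**How the efficacy analysis treats rescue.** In the primary endpoint row of SAP 7.4, Table 3: "platelet count assessments from the start date of rescue medication up until 4 weeks after the end date of rescue medication will be excluded".

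**What the model is for.** Protocol 5.1: "the pediatric PK/PD model will be updated with emerging data in order to confirm the appropriate dose of avatrombopag in each cohort". The footnote to Protocol Table 4 says initial doses in Cohorts 2 and 3 may be changed after modelling the previous cohort. Section 11.2.5 allows doses to be modified on PK/PD analysis of emerging data.

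**Where further detail sits.** SAP Section 1 defers PK/PD analysis to a separate plan, which is not among the documents.

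**The concern.** An exposure-response model should relate the platelet count to avatrombopag. A count raised by IVIg or a transfusion carries information about the rescue treatment instead. The protocol accepts that other ITP treatment can confound this model, because it drops counts after a background dose change. It then leaves out the rescue treatments that are new to the child.

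The contrast is plain for a single drug. A child whose baseline corticosteroid is increased as rescue loses all later counts from the model. A child not on corticosteroids at Baseline who is given one as rescue loses none.

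At stake is the exposure-response estimate used during the trial, when doses for the younger cohorts are confirmed or modified. The SAP's responder endpoints are not affected.

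**Working it through.** No figure in the documents is in dispute, so the check sets the rules side by side.

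| On-study event | Rescue under 8.6? | Triggers 11.2.5? | Later counts in PK/PD model, as written | Counts in primary endpoint (SAP 7.4) |
|---|---|---|---|---|
| Baseline ITP drug increased | Yes | Yes | All dropped | Out until 4 weeks after end |
| New corticosteroid | Yes | No | Not excluded | Out until 4 weeks after end |
| IVIg or anti-D | Yes | No | Not excluded | Out until 4 weeks after end |
| Platelet transfusion | Yes | No | Not excluded | Out until 4 weeks after end |
| Baseline ITP drug reduced (8.4) | No | Yes | All dropped | Kept |

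**Can the trigger be read to include new drugs?** No. It requires a permitted medication already taken at Baseline. IVIg, anti-D and platelet transfusion are not on the 8.3 list and are barred by 8.5 except as rescue. A newly started corticosteroid was not taken at Baseline.

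**Does another passage remove these counts?** None in the protocol or SAP does. The SAP's rescue window is written for the primary endpoint.

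**Do rescued children stay in the Core Phase?** They can. Under Protocol 5.3, rescue counts as lack of treatment effect only if needed more than 3 times or continuously for more than 3 weeks.

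**Scale for one rescued child on avatrombopag.** The documents give no rescue rate, so only a unit can be shown.

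- First-10 review: 10 × 3/4 = 7.5 children on drug; 7.5 × 10 weekly counts (Weeks 1 to 10) = 75 counts.
- Cohort 1 fully enrolled: 21 × 12 = 252 counts on drug.
- Assumption: a one-day rescue between two weekly visits. Add one count if it starts on a visit day and that day's count is included.

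| Window assumed | Source | Counts affected | Share of 75 | Share of 252 |
|---|---|---|---|---|
| 7 days | Platelet-transfusion washout, Protocol 8.5 | 1 (2) | 1.3% (2.7%) | 0.4% (0.8%) |
| 14 days | Inclusion criterion 7: immunoglobulin or rescue corticosteroid | 2 (3) | 2.7% (4.0%) | 0.8% (1.2%) |
| 4 weeks | SAP 7.4 | 4 (5) | 5.3% (6.7%) | 1.6% (2.0%) |

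These are shares of counts per rescued child. They do not measure bias, and multiplying them up would need a rescue rate that the documents do not contain.

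**Direction.** A rescue-driven rise in a child on avatrombopag sits at a positive exposure and can be read as drug effect. The same rise in a placebo child, if placebo counts enter the model at zero exposure, weakens the apparent drug effect. The documents fix neither the mix nor whether placebo counts are used, so the net sign is unknown.

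**The case against.** **The PK/PD SAP is unseen.** Protocol Section 11 only outlines methods, the covariate list in 11.2.5 is open, and 8.6 requires all rescue to be recorded with dose and frequency. The modeller could exclude or model rescue without breaching the protocol. This stands: silence in 11.2.5 does not show that the final model keeps these counts. The protocol rule is still incomplete, and a PK/PD SAP that merely repeats it would carry the gap.

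**The 4-week window is an efficacy convention.** It is not a documented duration of effect, and the protocol's own washouts are 7 and 14 days. This stands too, and is why the working shows a range.

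**The consequence is softened.** PK and safety data also inform the dose, formal model updates follow full enrolment of each cohort, adult data may be pooled, and each child's dose is titrated on platelet count. All true. This lowers the stakes without closing the gap.

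**Stronger readings that the documents do not support:**

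- *Rescue falls mainly on non-responders at high dose levels, so the model overstates the drug.* Protocol Table 3 makes this plausible, since low counts lead to a higher level. But 8.6 allows rescue at any time, moving from Level 4 to Level 6 takes about 4 weeks (two steps, 2 weeks each), children with lack of effect may leave the Core Phase, and placebo children may be rescued as well.
- *Dropping counts after a background reduction is an equal error, because it removes good responders.* Section 8.4 does say background drugs "may be down titrated in order to maintain the subject's platelet count between" the target limits, so the exclusion can depend on response. But dropping counts after a background change is a defensible way to avoid confounding, and the child's earlier counts stay in.

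**Conclusion.** The gap holds on the text. As written, 11.2.5 excludes counts after one kind of rescue in 8.6 and not after the other, while the SAP sets aside counts after both for the primary endpoint. If the rule is followed literally, rescue-driven counts enter a model that can modify doses in later cohorts, and they can distort the exposure-response estimate.

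The size and direction of any distortion cannot be derived from these documents. The per-child shares above rest on an assumed window and a one-day course, and the number of rescued children is unknown. A reader might infer that the plan credits IVIg or transfusion effects to avatrombopag. That goes too far: it assumes a direction, and it assumes that the separate PK/PD SAP leaves the matter open. The finding is an incomplete exclusion rule, not a demonstrated bias in the fitted model.

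**What to change.** 1. In Protocol 11.2.5, extend the exclusion to counts from the start of any rescue therapy in 8.6 until a stated window after its end. The SAP's 4 weeks is a natural choice because the plan already uses it. Keep the existing clause for background dose changes, and say that the longer exclusion applies where both are met.
2. Run one sensitivity fit with a shorter window based on the protocol's 7- and 14-day washouts.
3. Put the same rule in the PK/PD SAP and in the instructions for the interim modelling by the unblinded designee. If the PK/PD SAP already covers rescue, an aligning sentence or cross-reference in 11.2.5 is enough.
4. At most, add a sensitivity fit that keeps counts after a background reduction. A time-varying covariate for background dose is not recommended: it would span several drug classes in about 7 to 21 treated children per review or cohort and may not be estimable.

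The cost is a sentence in each document and one or two extra model runs. Rescue is already recorded in the eCRF. The downside is that some counts from rescued children leave the model. No dosing or rescue rule changes.

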11.3 Sample Size Estimation

The proposed sample size is based on the anticipated response rates for avatrombopag and placebo for the primary endpoint (durable response) and the alternative primary endpoint (platelet response for 2 consecutive weeks).

Based on the eltrombopag PETIT2 study conducted in pediatric patients with chronic ITP, the durable response rates were 41.3% and 3.4% for eltrombopag and placebo, respectively (Grainger, 2015). It is reasonable to assume that the treatment effect of avatrombopag will be very similar to that of eltrombopag, due to both drugs being in the same class, having similar mechanisms of action, and treating similar patient populations (e.g., patients aged ≥ 1 to <18 years with relapsed or refractory disease after 1 or more previous treatments for ITP and a Baseline platelet count $<30\times10^9$ /L). With the 3:1 ratio of avatrombopag to placebo, a total of 72 subjects (54 avatrombopag and 18 placebo) will provide at least 90% power to detect the treatment difference of 37.9% in durable response at $\alpha=0.05$, based on the Fisher's exact test.

In addition, a 12 week study of romiplostim in treating pediatric ITP patients showed that 88% of romiplostim treated subjects achieved a platelet count $\geq 50 \times 10^9 / L$ for 2 consecutive weeks (alternative primary endpoint for this study), whereas none of the placebo treated subjects achieved the same endpoint (Bussel, 2011). With the 3:1 ratio of avatrombopag to placebo, a total of 72 subjects (54 avatrombopag and 18 placebo) will provide $\geq 99\%$ power to detect the treatment difference of 80% in proportion of subjects achieving a platelet count $\geq 50 \times 10^9 / L$ for 2 consecutive weeks at $\alpha = 0.05$, based on the Fisher's exact test.

12 DATA MANAGEMENT AND RECORD KEEPING

12.1 Data Management

12.1.1 Data Handling

Data will be recorded at the site on eCRFs and reviewed by the CRA on an ongoing basis and during monitoring visits. The CRA will verify data recorded in the electronic data capture (EDC) system with source documents. All corrections or changes made to any study data must be appropriately tracked in an audit trail in the EDC system. An eCRF will be considered complete when all missing, incorrect, and/or inconsistent data has been accounted for and reconciliation between other databases (e.g., safety) is complete.

12.1.2 Computer Systems

Data will be processed using a validated computer system conforming to regulatory requirements.

12.1.3 Data Entry

Data must be recorded using the EDC system as the study is in progress. All site personnel must log into the system using their secure username and password in order to enter, review, or correct study data. These procedures must comply with Title 21 of the Code of Federal Regulations (21 CFR) Part 11 and other appropriate international regulations. All passwords will be strictly confidential.

12.1.4 Medical Information Coding

For medical information, the following thesauri will be used:

- MedDRA for medical history and AEs, and
- WHODrug Dictionary for prior and concomitant medications.

12.1.5 Data Validation

Validation checks programmed within the EDC system, as well as supplemental validation performed via review of the downloaded data, will be applied to the data in order to ensure accurate, consistent, and reliable data. Data identified as erroneous, or data that are missing, will be referred to the investigative site for resolution through data queries.

The eCRFs must be reviewed and electronically signed by the Investigator.

12.2 Record Keeping

Records of subjects, source documents, monitoring visit logs, eCRFs, inventory of study product, regulatory documents, and other Sponsor correspondence pertaining to the study must be kept in the appropriate study files at the site. Source data is defined as all information in original records and certified copies of original records of clinical findings, observations, or other activities in a clinical study necessary for the evaluation and reconstruction of the clinical study. Source data are contained in source documents (original records or certified copies). These records will be retained in a secure file for the period as set forth in the Clinical Study Agreement. Prior to transfer or destruction of these records, the Sponsor must be notified in writing and be given the opportunity to further store such records.

13 INVESTIGATOR REQUIREMENTS AND QUALITY CONTROL

13.1 Ethical Conduct of the Study

This study will be conducted in compliance with the protocol and all regulatory requirements, in accordance with Good Clinical Practice (GCP), including International Council for Harmonisation (ICH) guidelines, and in general conformity with the most recent version of the Declaration of Helsinki. Sobi Quality Assurance or designee may verify adherence to these practices and procedures through audit and inspection.

13.2 Institutional Review Board/Independent Ethics Committee

The IRB/IEC will review all appropriate study documentation in order to safeguard the rights, safety, and well-being of subjects. The study will only be conducted at sites where IRB/IEC approval has been obtained. The protocol, IB, ICF/assent, advertisements (if applicable), written information given to the subjects, safety updates, annual progress reports, and any revisions to these documents will be provided to the IRB/IEC by the Investigator.

The Investigator is obligated to keep the IRB/IEC informed of any unanticipated problems. This may include notification to the IRB/IEC of Investigational New Drug (IND) Safety Reports.

Federal regulations and ICH guidelines require that approval be obtained from an IRB/IEC prior to participation of subjects in research studies. Prior to study onset, the protocol, any protocol amendments, ICFs, assent forms, or advertisements to be used for subject recruitment, and any other written information regarding this study to be provided to a subject must be approved by the IRB/IEC.

The study will only start in the respective sites once the IRB's/IEC's written approval has been given. No study drug will be released to the site for dosing until written IRB/IEC authorization has been received by the Sponsor.

It is the responsibility of the Sponsor, or their designee, to obtain the approval of the responsible IRB/IEC according to national regulations.

13.3 Protocol Amendments

Any amendments to the study protocol will be communicated to the Investigator by the Sponsor or designee. All protocol amendments will undergo the same review and approval process as the original protocol. Substantial amendments must be approved as per local regulations prior to enrolling subjects. A protocol amendment may be implemented after it has been approved by the IRB/IEC, unless immediate implementation of the change is necessary for subject safety. In this case, the situation must be documented and reported to the IRB/IEC within 5 working days.

13.4 Informed Consent/Assent

The ICF and/or assent, and any changes to the ICF and/or assent made during the course of the study, must be agreed to by the Sponsor or designee and the IRB/IEC prior to its use and must be in compliance with all ICH GCP, local regulatory requirements, and legal requirements.

The Investigator must ensure that each study subject and/or subject's LAR, as applicable, is fully informed about the nature and objectives of the study and possible risks associated with participation and must ensure that the subject and/or the subject's LAR, as applicable, has been informed of his/her rights to privacy. The Investigator will obtain written informed consent and/or assent, as applicable, from each subject and/or the subject's LAR, as applicable, before any study-specific activity is performed and should document in the source documentation that consent was obtained prior to enrollment in the study. The original signed copy of the ICF/assent must be maintained by the Investigator and is subject to inspection by the Sponsor, their representatives, auditors, the IRB/IEC, and/or regulatory agencies. A copy of the signed ICF/assent will be given to the subject and/or the subject's LAR, as applicable.

